Data management will be responsible for monitoring interviews completed, which will be done monthly. The interviewers will be sent a list of interviews that have not yet been completed with study participants. This process differs from query letters which request information on specific data items within a form.

Data management will periodically conduct an audit program. A random subset of cases will be selected from the files. In this way, problems with data collection and transmission can be detected early. In addition, data will be monitored for secular trends in data completeness and quality. Study audits will be conducted several times over the course of the study.

Only the study generated ID will used for any and all references to records for purposes of cleaning and overall quality.

***Ame00068213

We added the University of Michigan IRB to the language about the HIPAA waiver for recruitment and language about the HIPAA authorization for enrolled participants recruited from the Detroit Medical Center.

Study Statistical Design

Sample Size Determination:

The primary outcomes of interest in the randomized trial are ED visits and hospitalizations, both overall and heart related. In a sample of 443 patients at a 12 month follow-up, there were significant differences between those that received "take PRIDE" and those that did not in hospitalizations overall (difference of 0.26 times hospitalized) and heart related hospitalizations (difference of 0.41 times hospitalized) and also in overall ED visits (difference of 0.17 visits). The secondary outcome of interest is cardiac symptom experience: number, frequency, and bothersomeness. Several cardiac symptoms will be summed to obtain overall scores: chest pain, shortness of breath, waking with chest pain, waking with shortness of breath, and palpitations. In a sample of 460 patients randomized to the intervention or usual care, researchers found that the change in the number and frequency of symptoms differed significantly between the intervention and comparison group (difference of 0.36 and 1.16 in scores, respectively).

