To detect a 0.15 difference in the change in the number of overall ED visits between the intervention and comparison groups at a 12 month follow-up, a sample size of 188 will be necessary in the intervention and comparison groups for a total sample size of 376 at the end of 12 months. This number will be sufficient to detect a 0.20 difference in hospitalizations and will also be sufficient to detect differences in cardiac symptoms. In a recent iteration of the intervention, the recruitment response rate was 48% and the loss to follow-up was about 20%. Therefore, 1300 subjects will be contacted for participation and 376 subjects will be enrolled.

Analysis of patient outcomes:

Descriptive statistics will be computed for all outcomes overall and stratified by randomized study arms. Health care utilization: Outcome variables including hospitalizations and ED visits will first be assessed as dichotomous variables and will be analyzed using chi-square analyses followed by logistic regression modeling. Because these are count variables, Poisson regression analyses will also be conducted. Cardiac symptoms: The presence of cardiac symptoms will be assessed individually using chi square tests and logistic regression modeling. The cardiac symptoms will also be summed to obtain an overall score of symptoms as well as a score for the frequency and severity. These will be continuous and will be analyzed using analysis of covariance (ANCOVA) and multiple linear-regression modeling assuming normal distributions. If necessary, transformation will be used to ensure normality or Poisson regression will be used if Poisson distributions are found for these variables. They may also be recoded as categorical or ordinal variables and analyzed using chi-square tests and multiple or cumulative logistic regressions.

Functional health status: Functional health status will be assessed using the PROMIS Global Health Scale and/or PROMIS-29. The scores are continuous variables and will be analyzed similarly to the symptoms using ANCOVA and linear regression modeling where the normality assumption is appropriate. They may also be re-coded as categorical or ordinal variables and analyzed using chi-square tests and logistic regressions.

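### The trial is sized on the number of ED visits and hospitalizations, but the plan lists an any/none analysis first and never says that the count comparison decides

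*Combined protocol and SAP*

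**What the plan says.** Under Study Statistical Design, Sample Size Determination, the endpoints are set out thus: "The primary outcomes of interest in the randomized trial are ED visits and hospitalizations, both overall and heart related". Every planning figure given for them is a mean number of events. The earlier results are a "difference of 0.26 times hospitalized", 0.41 for heart-related hospitalizations and 0.17 for ED visits. The size follows from a count: "To detect a 0.15 difference in the change in the number of overall ED visits between the intervention and comparison groups" at 12 months, "a sample size of 188 will be necessary in the intervention and comparison groups for a total sample size of 376 at the end of" the 12 months. For the other endpoint: "This number will be sufficient to detect a 0.20 difference in hospitalizations". No proportion of participants with any visit appears.

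Under Analysis of patient outcomes, the order is different: "Outcome variables including hospitalizations and ED visits will first be assessed as dichotomous variables and will be analyzed using chi-square analyses", and then logistic models. The next sentence is: "Because these are count variables, Poisson regression analyses will also be conducted". The Change over time paragraph adds GEE for discrete outcomes, with a time-by-program interaction in all models. It does not say whether visits enter as counts or as any/none. No analysis is called primary.

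**The concern.** The sample size and the first-listed analysis are on different scales. Any/none scores one visit and six visits alike, so it does not estimate the difference in number of visits for which 188 per arm was chosen. It is also blind to a program that turns three visits into one. Because the plan ranks nothing, its only ordering is that any/none comes first and the count model is added. A reader who follows that order could take a null chi-square as evidence of no benefit although the number of visits had fallen.

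**Working it through.** **Inputs from the documents.** 188 per arm; a difference of 0.15 ED visits. Not given: alpha, power, SD, event rate, overdispersion. I assume a two-sided 5% level and show a range for the rest.

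**The plan's own figure.** 188 cannot be reproduced without an SD. Solving backwards, SD = 0.15 / [(1.960 + z_power) × √(2/188)]. This gives 0.519 at 80% power (z_power = 0.842) and 0.449 at 90% (z_power = 1.282). An SD of 0.519 is a variance of 0.269. Read as a Poisson variance for the control arm, that is a control mean of about 0.27. Read as the average variance of the two arms, it is close to a control mean of 0.35, since (0.35 + 0.20)/2 = 0.275. Control means of about 0.27 to 0.35 are therefore where the stated size is roughly adequate for the count.

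**Method.** Control mean m1, program mean m2 = m1 − 0.15.
- Probability of any visit: p = 1 − exp(−m) for Poisson, or 1 − (1 + m/k)^(−k) for negative binomial with shape k.
- Variance of the count: v = m, or m + m²/k.
- Efficiency of any/none relative to the count: [(p1 − p2)² / (p1q1 + p2q2)] / [0.15² / (v1 + v2)], with q = 1 − p.
- Power from the normal approximation at 188 per arm.

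**One case in full** (m1 = 0.35, Poisson). p1 = 0.2953, p2 = 0.1813, difference 0.1140, summed binomial variance 0.3565. Any/none: 0.1140²/0.3565 = 0.0365. Count: 0.0225/0.55 = 0.0409. The ratio is 0.89, a loss of about 11%.

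| Control mean | Distribution | Count power | Any/none power | Efficiency |
|---|---|---|---|---|
| 0.27 | Poisson | 90.9% | 89.2% | 94.2% |
| 0.27 | k = 0.5 | 78.1% | 71.9% | 86.0% |
| 0.30 | Poisson | 86.6% | 83.7% | 92.2% |
| 0.30 | k = 1 | 78.3% | 72.3% | 86.5% |
| 0.35 | Poisson | 79.2% | 74.5% | 89.2% |
| 0.40 | Poisson | 72.3% | 66.0% | 86.4% |
| 0.40 | k = 0.5 | 50.2% | 38.8% | 72.5% |
| 0.60 | Poisson | 51.9% | 42.1% | 76.9% |
| 0.60 | k = 0.5 | 28.6% | 19.2% | 60.7% |
| 1.00 | Poisson | 32.7% | 21.9% | 61.1% |
| 1.00 | k = 0.5 | 14.5% | 9.5% | 47.6% |
| 1.50 | Poisson | 23.0% | 13.0% | 45.2% |
| 1.50 | k = 0.5 | 9.5% | 6.7% | 38.6% |

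The first five rows, where the count has roughly 80-90% power, show losses of about 6-14%. The remaining rows show about 14% to about 60%. At a mean of 1.0 (Poisson), 80% power needs 646 per arm for the count and 1,057 for any/none. The low end depends on the scale: on the log-rate scale the Poisson loss is 1 − m/(e^m − 1), which is 13% at m = 0.27.

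**Where the effect falls only on single visits.** Take m1 = 1.0, k = 0.5. Then P(0) = 3^(−0.5) = 0.577 and P(1) = 0.577 × 0.5 × (1/1.5) = 0.192. If the program prevents the only visit in 15% of participants, the mean again falls by 0.15. The any-visit proportion goes from 42.3% to 27.3%, and the count variances are 3.00 and 3.13. Power is 87% for any/none and 13% for the count.

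**Ordinary Poisson standard errors.** At m = 1.0, k = 0.5 the variance-to-mean ratio is 3. Ignoring it, the false-positive rate is 2 × [1 − Φ(1.96/√3)] = 26% instead of 5%.

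All of these figures compare 12-month counts. The plan sizes on change, so they are illustrative.

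**The case against.** The strongest reply is that the order may only be an order of work. The plan commits to Poisson regression in the next sentence and to GEE with a time-by-program term afterwards, which is the natural form for a difference in change. A reader might infer from the opening sentence that any/none is the primary analysis, or that the plan cannot detect fewer repeat visits at all. The documents support neither: no primary analysis is named, and the plan as a whole includes at least one count model. What stands is that nothing says the count model decides, and that the GEE text leaves the form of the outcome open.

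The second reply concerns size, and most of it stands. A reader might infer a loss of 15-60% as a property of this plan. That range needs assumed control means of about 0.4 to 1.5, at which 188 per arm is already too few for the count itself. Much of the shortfall there is a sizing problem.

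Third, the choice depends on how the program works. If 40% use the ED in both arms and users average 2.5 against 2.125 visits, any/none has only its 5% error rate, but that is true by construction. The single-visit case above reverses the ranking.

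Fourth, any/none is not exposed to overdispersion, whereas ordinary Poisson standard errors are. That is an argument about how to fit the count analysis and does not justify leading with another quantity.

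**Conclusion.** The concern holds in a limited form. The target and the 188 per arm are set on numbers of events. The first-listed analysis is on any/none, the count model is an addition, and none is designated primary. Any/none does not estimate the planned quantity and cannot see fewer repeat visits among people who still have one.

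The loss cannot be fixed from the documents, because they give no event rate. For a general downward shift in Poisson or negative binomial counts, it is modest (about 6-14%) where the stated size is roughly adequate for the count. It is larger (about 14-60%) at assumed control means of 0.4-1.5, where the count test also misses 80%. The count was the more efficient in every such scenario, but not if the program mainly prevents single visits. The case for leading with the count therefore rests first on matching the analysis to the quantity sized, and only second on power.

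**What to change.** In Analysis of patient outcomes (Health care utilization), state that the conclusion for ED visits and hospitalizations is drawn from the between-arm comparison of the number of events. Because the sizing is on change, either adjust that comparison for the baseline count or use the time-by-program term of the GEE in Change over time, stating that it is fitted to the counts. Specify a negative binomial model or robust (sandwich) standard errors in place of ordinary Poisson ones. Keep the any/none chi-square and logistic analyses as descriptive support, and say that the trial was not sized for them.

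The cost is SAP wording. Count and any/none analyses are both already planned on the same data, and the stated 188 per arm is unaffected. Two small downsides: the result that is simpler to explain no longer leads, and intervals that allow for overdispersion may be wider.

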Additionally, a postcard will be included in the recruitment package for each patient to return to the project director should they not want to be contacted by the researchers. The cover letter will also inform the patient that if they do not decline participation, they will receive a telephone call from a member of the research team to describe the study and determine their interest in participating.

These potential participants will not be asked directly about the presence of terminal illness with a prognosis of a year or less (an exclusion criterion that will be applied when DMC is screening EMR), as it is assumed that people who pro-actively call in to inquire about the program feel that they could benefit from the it and would not have a severely life-limiting illness.

Eligibility criteria for participants are as follows:

- 50 years or older
- One or more diagnosed cardiovascular conditions, including:
 - Atrial fibrillation

- Angina
- Myocardial infarction
- Congestive heart failure
- Valvular disease (aortic stenosis or mitral regurgitation)
- Peripheral vascular disease
- Pulmonary hypertension
- OR >2 major risk factors for CVD (high cholesterol, high blood pressure, smoking, diabetes, chronic kidney disease-stage 3 or 4)
- Must have access to a mobile or landline telephone
- Must be able to travel to group sessions, with or without transportation assistance

Exclusion Criteria

Limited fluency in English posing significant barrier to deriving program benefit

Screening, consent, and enrollment procedures:

Focus groups: Screening and enrollment procedures are described above. We will ask participants to sign informed consent, including consent to audio record, on site at the group, and will go over the form together as a group.

Pilot Study

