Throughout recruitment calls, each patient will be encouraged to ask questions and told that they are free to withdraw from the study at any time, for any reason. A toll-free [contact]) will be provided so that potential participants can call the research office with additional questions at any time.

Randomization will be stratified by four categories of a risk score based on data from prior studies that includes age, gender, and number of comorbidities, using responses from the baseline interview. To reduce the predictability and resulting bias due to block randomization, random block sizes (e.g., lengths of 8, 10, 12 subjects) will be used and blinded to investigators. Prior to recruitment, a permuted block randomization schedule will be created using the RANTBL and RANUNI functions in SAS to generate blocks with varying sizes of 8, 10, or 12 and random numbers for group assignment within each of the 4 categories of risk score.

Once enrolled, participants recruited through the Detroit Medical Center (DMC), will be asked to complete another consent document that includes a HIPAA Authorization statement. This will authorize DMC to release specific health information related to Take Heart after the recruitment phase (first, middle and last name, street address, city, state, zip code, email address, home and cell phone number, primary care provider and specialist, number of visits to the emergency department and hospitalizations during the year prior to the Take Heart study and the year of your participation in the study), to the University of Michigan School of Public Health research staff.

WHAT HAPPENS TO SUBJECTS DURING RESEARCH:

Focus groups:

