Intervention dose received: The dose of the intervention will be examined using the logs completed by the health educator. The subject will receive one point for each of 4 sessions attended and a point for each of the three components completed: goal setting, tracking form, and the judgment/reaction. The scores will only be available for the intervention group and will describe average level of participation within the intervention group using frequencies and mean scores.

The components of the intervention: Observation, judgment, goal setting strategies, outcome expectancy and efficacy can also be described individually. Participants in the intervention group may be stratified based on the dose score and outcomes compared using t-tests or chi-square tests of homogeneity to describe impact of dose on outcomes. Instrumental variable approaches to estimating the complier-average causal effect of the intervention will be applied, with compliance defined using two different choices of cut-off on the performance score.

Change over time: The focus of the mixed-model (for continuous outcomes) and GEE (for discrete outcomes) analyses will be to assess changes in dependent measures over time, and whether these changes differ between program participants and "usual care" controls. The effect of time as well as the interaction between time and program participation (program vs. waitlist control) will be included as factors in all models.

Generalizability of the intervention: To determine how effective the intervention would be if duplicated in a similar population, it will be important to examine non-consenters to see if those who choose to participate have certain factors that may be correlated with improved outcomes not present in those who do not participate. Aggregate data from the DMC including demographics, and health care use values will be obtained on those patients that meet the criteria for participation but were not enrolled in the randomized controlled trial to be compared to enrolled participants using t-tests and chi-square tests to discover any differences.

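### The Poisson regression planned for the primary ED-visit and hospitalization counts makes no allowance for variance above the mean

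*Combined protocol and SAP*

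**What the plan says.** Under Sample Size Determination: "The primary outcomes of interest in the randomized trial are ED visits and hospitalizations, both overall and heart related". Under Analysis of patient outcomes, these outcomes "will first be assessed as dichotomous variables and will be analyzed using chi-square analyses followed by logistic regression modeling". The count analysis follows in one sentence: "Because these are count variables, Poisson regression analyses will also be conducted". No scale parameter, robust variance, negative binomial alternative or comparison of variance with mean is given for them anywhere.

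In the same section, the secondary symptom scores do carry a condition: "Poisson regression will be used if Poisson distributions are found for these variables". Descriptive statistics are planned for all outcomes, but no rule connects them to the choice of count model.

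Three other places bear on the point:

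- **Eligibility criteria.** The list of diagnosed conditions includes "Congestive heart failure", and a person can also enter through "OR >2 major risk factors for CVD".
- **Main Study, randomization paragraph.** "Randomization will be stratified by four categories of a risk score"; the components named are age, gender and number of comorbidities.
- **Change over time.** The focus of the "GEE (for discrete outcomes) analyses will be to assess changes in dependent measures over time", with no family, scale or variance estimator stated.

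**The concern.** A Poisson model ties the variance to the mean. That an outcome is a count does not make this true. Yearly ED visits and admissions vary between people for lasting reasons such as type and severity of disease, and such variation pushes the variance above the mean. The eligibility criteria span a wide range of underlying risk, so some excess is to be expected.

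If it is present within randomization strata, standard errors computed with the scale fixed at 1 are too small, confidence intervals are too narrow, and the test rejects a true null too often in both directions. This affects the regression the SAP names for the number of ED visits, and the sample size is set on a difference in the change in that number.

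**Working it through.** **Inputs from the documents.** 188 per arm, 376 in total, and about 20% loss to follow-up (Sample Size Determination). The text gives 376 both at 12 months and as the number enrolled. I therefore used 188 per arm and also about 150 per arm (376 × 0.80 = 300.8, or 301 in total).

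**The plan's own figure.** The 188 per arm cannot be reproduced, because alpha, power and SD are not stated. With two-sided 5% and 80% power (assumed), it implies an SD of change of 0.15 / [(1.960 + 0.842) × √(2/188)] = 0.519. This says nothing about dispersion, since no mean is given, and nothing below depends on it.

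**Assumed inputs.** Within-stratum variance/mean ratio φ of 1, 1.25, 1.5, 2 and 3; mean counts of 0.25, 0.5 and 1.0.

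**Step 1: formula.** With arm totals Sₐ and S_b, plain Poisson takes the variance of the log rate ratio as 1/Sₐ + 1/S_b. The true value is φ times that. The test statistic therefore has SD √φ under the null, and the true error is 2 × [1 − Φ(1.96/√φ)]. For φ = 1.5: 1.96/1.225 = 1.600, and 2 × 0.0548 = 0.110. The correct interval is √φ times as wide as the Poisson one.

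| φ | True two-sided error | False benefit (half) | Coverage of 95% CI | √φ |
|---|---|---|---|---|
| 1 | 5.0% | 2.5% | 95.0% | 1.000 |
| 1.25 | 8.0% | 4.0% | 92.0% | 1.118 |
| 1.5 | 11.0% | 5.5% | 89.0% | 1.225 |
| 2 | 16.6% | 8.3% | 83.4% | 1.414 |
| 3 | 25.8% | 12.9% | 74.2% | 1.732 |

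**Step 2: simulation.** Gamma-Poisson counts, no treatment effect, 40,000 trials per setting, both arm sizes. Plain Poisson error was 4.7–5.1%, 7.6–8.0%, 10.5–11.1%, 15.8–16.6% and 25.2–25.9% for φ of 1, 1.25, 1.5, 2 and 3. This agrees with the formula.

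**Step 3: effect of stratification.** Take four equal strata with rates 1:2:4:8 (assumed). Their mean is 3.75 and their mean square 21.25, so CV² = 21.25/14.06 − 1 = 0.51. Overall variance/mean is 1 + mean × CV², which is about 1.26 at mean 0.5 and 1.51 at mean 1.0. With no excess inside strata, the simulated error stays at 5.1%. With within-stratum φ of 1.25, 1.5, 2 and 3, it returns to 7.5–8.1%, 10.6–10.8%, 16.4–16.7% and 25.4–26.1%. Only within-stratum excess does the damage.

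**Step 4: the alternatives, φ 1.25 to 3.**

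| Method | Simulated error |
|---|---|
| Any/none chi-square | 4.8–5.7% |
| Negative binomial (means 0.5 and 1.0) | 4.7–5.7% |
| Poisson, sandwich variance, 188 per arm | 4.8–6.4% across runs |
| Poisson, sandwich variance, 150 per arm | at most 6.7% |
| GEE time-by-arm, sandwich errors | 4.9–5.7% |
| GEE, exchangeable, estimated scale | 4.7–5.4% |
| GEE, exchangeable, scale fixed at 1 | 7.7–26.2% |

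The worst sandwich-Poisson case is mean 0.25 with φ = 3. The GEE rows assume two time points and half of participants keeping the same rate.

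**The case against.** **The SAP is brief, and naming Poisson regression does not exclude a scale or robust option.** True, but without such an option Poisson regression means scale 1. Adding one after the data are seen lets the model be chosen with the result in view.

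**The contrast with the symptom scores is weak.** Poisson is a fallback there, so conditional wording came naturally. This is fair, and the contrast is not proof of oversight. The missing provision for the primary counts does not depend on it.

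**The count model is supplementary.** The any/none analyses come first, and the sample-size target is a difference in change, which the GEE matches more closely. This stands as a limit on the damage. But the plan does not say which analysis decides, any/none tests do not estimate a number of visits, and the GEE is safe only under settings the plan does not state.

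**The upper figures have no anchor.** Under the gamma model, φ = 1 + mean × CV² of individual rates. For φ = 3, the residual CV² must be (3 − 1)/mean, or 8, 4 and 2 at means 0.25, 0.5 and 1.0, against 0.51 for the eight-fold strata above. That is roughly 4 to 16 times as much heterogeneity left within strata as was assumed between them. Rarer events, such as heart-related ones, also bring φ closer to 1, and prognostic covariates would lower it. This largely stands: 17% and 26% mark the far end of the range. The lower end asks less: φ = 1.5 at mean 1.0 needs a residual CV² of 0.5.

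**Conclusion.** The concern holds and should be fixed. The plan applies a model that requires variance equal to mean to its primary counts and gives no reason to expect that equality. Even φ = 1.5 roughly doubles the nominal error, to 11%. The figures from 8% to 26% rest on assumed within-stratum dispersion, because the documents contain no variances, and the upper half of that range needs large residual heterogeneity. Some residual excess is likely, because the stated parts of the stratification score count comorbidities without saying which condition a person has. This is a judgement and not a measured quantity, so confidence is medium. The bias is in the stated precision: the error favours neither arm. The any/none tests and a sandwich-based GEE remain valid, which keeps this below a critical fault.

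**What to change.** In Analysis of patient outcomes, replace plain Poisson for ED visits and hospitalizations with one method named in advance: negative binomial regression, or Poisson regression with sandwich variance. Negative binomial held its level in the settings run but relies on its distributional form. The sandwich does not, but runs slightly high when counts are sparse and dispersion is large. Under Change over time, state that the GEE for counts uses sandwich errors.

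The cost is one model option and one sentence, with no new data and no change to the planned sample size. Intervals become about 12%, 22%, 41% and 73% wider at φ of 1.25, 1.5, 2 and 3, which is the uncertainty actually present. If there is no overdispersion, the loss is negligible: sandwich standard errors are 0.996–0.997 of the Poisson ones, and negative binomial ones 1.013–1.015.

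The team should know that valid errors also show the true power. In an illustration with assumed means of 0.5 and 0.35 at 188 per arm, power is 60%, 44%, 35% and 25% at φ of 1, 1.5, 2 and 3. The fix does not cause that loss; plain Poisson would hide it.
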